This pilot protocol examines the change in the airway microbiome after azithromycin over an 8 week period. 40 subjects with poorly controlled asthma and 10 control subjects with no known lung disease will undergo clinical data collection including ACT score, lung function, exhaled nitric oxide (FeNO), methacholine challenge, and induced sputum and blood collection. Participants with asthma then are randomized 1:1 to receive azithromycin, 250 mg, or placebo, daily for 8 weeks. Clinical parameters including ACT, oral wash, adherence, side-effect profile, spirometry, and biological specimens (sputum, blood, FeNO) are collected again at 4 and 8 weeks. Control subjects undergo the same measurements, but do not receive any intervention.

Schedule of Events

	Asthma (A) or Control (C)	Visit 1/Week 0 (Screening) (+/- 3 days)	Visit 2/Week 4 (+/- 3 days)	Week 6 (+/- 3 days)	Visit 3/Week 8 (+/- 3 days)	Week 10 (+/- 3 days)	Visit 4/Week 12 (+/- 3 days)	Week 14 (+/- 3 days)
Informed Consent	A,C	X						
Site Visit	A,C	X	X		X		X	
Phone Call	A			X		X		X
Confirmation of Eligibility	A,C	X	X					
Randomization	A		X					
Drug Dispensation	A	X ^{1,2}	X ^{1,2,3}		X ^{1,2,3}		X ^{1,2}	
Demographics	A,C	X						
Medical History Review	A,C	X						
Asthma History	A	X						
Smoking History	A,C	X						
Concomitant Medication Review	A,C	X	X		X		X	
Physical Exam/Vital Signs	A,C	X	X		X		X	
Asthma Control Test	A	X						
Demographics Questionnaire	A,C	X						
Family History Questionnaire	A,C	X						
Work Exposures Questionnaire	A,C	X						
Home Exposures Questionnaire	A,C	X						
Physical Activity Questionnaire	A,C	X						
Secondhand Smoke Exposure Questionnaire	A,C	X						
Peak Flow Meter Readings ⁵	A	X	X	X	X	X	X	X
Electronic Diary ⁴	A	X	X	X	X	X	X	X
ECG	A,C	X	X		X		X	
Spirometry with Reversibility ⁶	A,C	X	X		X		X	
Exhaled NO	A,C	X	X		X		X	
Urine Pregnancy Test ⁷	A,C	X						
Methacholine Challenge ⁸	A,C	X	X		X		X	
Sputum Induction	A,C	X	X		X		X	
Oral Wash	A,C	X	X		X		X	
Complete Blood Count with Platelet Count and Differential Blood Sample	A,C	X			X			
Serum IgE Blood Sample	A,C	X						
RAST Blood Analysis	A,C	X						
Research Blood Samples	A,C	X			X			
Adverse Events Review	A,C		X	X	X	X	X	X
Compliance/Adherence to Diary and Study Drugs	A	X	X	X	X	X	X	X

1. Dispensation of albuterol to asthmatic subjects (if required at Visit 2 and Visit 3)
2. Dispensation of ICS/LABA to asthmatic subjects
3. Dispensation of azithromycin/placebo to asthmatic subjects

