Poisson modeling of relative abundance. To test for differences in relative abundance of key microbial genera between the placebo and azithromycin groups at each time point and over time, we will fit a Poisson regression model with treatment and time as fixed effects with offset (for the total abundance) and with subjects as random effects for the microbial genera of interest (72). Since missing data may be present in the data set, we will create a multiple imputation simulation function in R for generalized linear mixed effects models to improve efficiency of inference and to assess sensitivity of the model over multiple imputations using the R package mice. We will use the specific Poisson regression model to impute the missing values to obtain further efficiency in the data analysis. Based on the Poisson regression model fit, we will make inference for alpha, beta, and gamma diversity measures. These measures will be calculated using either Shannon entropy or the inverse Simpson index (in this context, the habitats of the microbiome genera are the samples collected on the treatment groups over time). Power and sample size calculations for the U01 RCT will be performed based on the fitted Poisson and multivariate regression models. If a test statistic is not significant in the pilot study, we will use mathematical statistical properties of the test statistics (such as the likelihood-ratio, the Wald test, or the score test statistics) under the alternative hypothesis which will allow us to generate power as functions of the sample size. We will create an R package in which we implement all statistical methods in the data analysis work-flow and create R markdown files with fully reproducible data analyses and description of statistical methods. In this way, the data analysis can be easily replicated. If new statistical methods are developed as a result of this complex multi-faceted data analysis, we will write a methodological paper for submission to a statistical journal.

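### Imputing missing counts from the Poisson analysis model yields no efficiency, and if the completed data reach the planned t-tests the standard errors are about 20% too small at an assumed 20% missing

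*Combined protocol and SAP*

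**What the plan says.** Under Poisson modeling of relative abundance, the analysis of key genera is set out thus: "we will fit a Poisson regression model with treatment and time as fixed effects with offset (for the total abundance) and with subjects as random". In other words, it is a Poisson mixed model with one random term per subject. The missing-data plan is multiple imputation: "we will create a multiple imputation simulation function in R for generalized linear mixed effects models to improve efficiency of inference". A second stated purpose is to see how the model holds up across imputations, and the software named is mice. The next sentence names the imputation model: "We will use the specific Poisson regression model to impute the missing values to obtain further efficiency in the data analysis".

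The section names no predictor beyond those in the analysis model. It does not give the missingness assumption, the number of imputations, whether parameters are redrawn for each imputation, the pooling rule, or the offset for a sample that does not exist. The results are carried forward: "Power and sample size calculations for the U01 RCT will be performed based on the fitted Poisson and multivariate regression models".

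The plan also has t-tests on the same kind of outcome. Effect of treatment on clinical outcomes plans two-sample t-tests on within-subject change to 8 weeks and refers to the listed outcomes. Those include the relative proportions of the ten leading genera (Outcome Measures). Initial microbiome analysis plans Student's t-test for relative percentages. Neither place says whether observed or completed data are used.

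**The concern.** Imputing an outcome from the model that will analyse it adds no information, so the stated reason for doing it is unsound. The draws also inherit the model's variance. A Poisson model with only a subject random effect treats two samples from one patient as differing by counting noise alone. If real samples vary much more than that between visits, the filled-in values are too regular, and any analysis that estimates variance from the completed data will understate it.

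At stake are the intervals and false-positive rate for the genus response to azithromycin, and the variability passed to the future RCT, which is objective (b) of the pilot.

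**Working it through.** **Inputs.** From the documents: 40 asthma subjects randomised 1:1, so 20 per arm (Study Design); Pseudomonas abundance 10.4 ± 1.8% and correlation ρ = 0.7 or 0.5 (Power calculations). Assumed: 10,000 reads per sample (a depth mentioned under Initial microbiome analysis), 10-30% of post-baseline values missing, 20 imputations, no true effect.

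**1. Reading 1.8 as an SD.** The plan gives no missing-data figure to reproduce, but its power figures test this reading. SD of change = 1.8 × √(2(1−ρ)) = 1.39 (ρ = 0.7) or 1.80 (ρ = 0.5). A paired t-test with n = 20 gives detectable changes of 0.92 and 1.19 (plan: 0.9 and 1.2) and half-widths of 0.65 and 0.84 (plan: 0.7 and 0.84). The reading fits.

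**2. Efficiency.** Three-visit Poisson mixed model, 20 per arm, 2,000 runs, 25% of post-baseline samples missing, Poisson model true:

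| Method | Empirical SD | Mean reported SE | 95% coverage |
|---|---|---|---|
| Likelihood, observed samples only | 0.0158 | 0.0156 | 94.8% |
| Multiple imputation, parameters redrawn, Rubin's rules | 0.0159 | 0.0157 | 94.4% |
| Multiple imputation, parameters not redrawn | 0.0158 | 0.0146 | 93.0% |
| One random imputation treated as real | 0.0165 | 0.0138 | 89.6% |

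No version has a smaller empirical SD than the likelihood fit. Proper imputation reports the right SE; only improper or single imputation understates it.

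**3. Real spread against Poisson spread.** Within-subject variance = 1.8² × (1−ρ) = 3.24 × 0.3 = 0.97, or 3.24 × 0.5 = 1.62 (percentage points squared). Poisson: 10.4% of 10,000 reads is 1,040 counts, SD √1,040 = 32.2 counts = 0.322 points, variance 0.104. Ratios: 0.972/0.104 = 9.3 and 1.62/0.104 = 15.6.

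**4. Effect on the Poisson fit.** With that extra variation in the data (three visits, 20-30% missing), reported SE over true SD was 0.29 (ρ = 0.7) and 0.24 (ρ = 0.5), and type I error 52-61%, the same with and without imputation. The empirical SD was also unchanged (0.0531 both ways at ρ = 0.7; 0.0633 against 0.0634 and 0.0682 against 0.0683 at ρ = 0.5).

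**5. Effect on a t-test of completed changes.** Hand calculation, baseline and final visit, 20% missing, 16 of 20 observed per arm:
- Variance of a real change: 2 × 0.972 = 1.944, or 2 × 1.62 = 3.24.
- Variance of an imputed change: about 2 × 0.104 = 0.208 (the draw plus uncertainty in the subject's rate).
- True SE: √(2 × 1.944/16) = 0.493, or √(2 × 3.24/16) = 0.636.
- Variance of the completed changes: 0.8 × 1.944 + 0.2 × 0.208 = 1.597, or 0.8 × 3.24 + 0.2 × 0.208 = 2.634.
- Reported SE: √(2 × 1.597/20) = 0.400, or √(2 × 2.634/20) = 0.513. Ratio to the true SE: 0.81 in both cases.
- Type I error: 2 × [1 − Φ(1.96 × 0.81)] ≈ 11%.

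The ratio is close to 1 minus the fraction missing, so 10% and 30% missing give about 8% and 16-17%. This omits the between-imputation variance, which is small. Simulations with parameters redrawn and Rubin's rules (1,500 null trials per setting) include it:

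| Missing | Type I error, imputed | Type I error, complete cases |
|---|---|---|
| 10% | 7-8% | 4-6% |
| 20% | 10-12% | 4-6% |
| 30% | 15-18% | 4-6% |

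At 20% missing the reported SE was 0.42 (ρ = 0.7) or 0.53 (ρ = 0.5), against a true SE of 0.51-0.53 or 0.64-0.65. Three-visit simulations at 20-30% missing gave 9-15%. Imputing with visit-level variation brought the SE ratio back to 0.92-0.97.

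**The case against.** The strongest reply is that the plan specifies multiple imputation, and when the imputation and analysis models agree, pooled standard errors are correct. Step 2 confirms this. A reader might infer that using one model for both tasks is what makes the Poisson standard errors too small, so that dropping imputation would cure them. The documents do not support that: step 4 shows the same understatement either way, caused by the Poisson variance. Silence on parameter draws and pooling is an unspecified risk, not a stated error.

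It is also fair that the imputation is tied to generalized linear mixed models, and nothing says expressly that imputed counts enter the t-tests. The t-test result is therefore conditional. Nothing rules that use out, however, and the imputation sentence speaks of the data analysis in general.

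The added efficiency might be meant relative to a generic mice imputation, or to complete cases: with a mid-treatment visit, imputation lowered the empirical SD by about 3-4% against complete-case change scores. A likelihood fit of the planned model captures that information without imputation.

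A reader might also infer that sputum goes missing because bacterial load is low, so that missing-at-random fails. The documents do not say so, and the plan does not claim a missing-not-at-random analysis. Finally, the protocol calls itself exploratory, and the primary ACT comparison is untouched.

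**Conclusion.** The efficiency rationale is unfounded: with no auxiliary variables and data missing at random, imputing from the analysis model gains nothing over fitting that model to the observed samples. The imputation is not the cause of the Poisson fit's small standard errors.

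The narrower harm is real but conditional. If completed data feed the t-tests on genus change, standard errors are about 20% too small at 20% missing and type I error is about 10-13%; about 7% at 10% missing and 15-18% at 30%, the last from the two-visit layout. This rests on 1.8 being an SD, 10,000 reads, the assumed missingness rates and 20 imputations. Repeating draws from one model shows only the variation that this model allows, so it is a weak test of sensitivity to missing data.

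**What to change.** - Delete both statements that imputation improves efficiency.
- Make the main genus analysis a likelihood fit to all observed samples, with visit-level (extra-Poisson) variation in the model. Without that term, removing imputation changes nothing.
- Keep multiple imputation as a sensitivity analysis only. State the missing-at-random assumption, visit-level variation in the imputation model, parameters redrawn each time, the number of imputations, Rubin's rules and the offset for a missing sample.
- Use auxiliaries already collected that exist when sputum does not: same-visit oral wash and FEV1. Sputum qPCR load comes from the sputum itself, so it helps only where sequencing alone failed.
- State whether the t-tests on genera use observed or completed data.
- Optional: a version that shifts imputed values in the azithromycin arm.

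The cost is SAP wording and a little more programming. Intervals will be wider than the planned analysis would report. That reflects variation the Poisson model leaves out; the estimates themselves become no less precise to any material degree.
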